2.4 ANALYSIS TIMING FOR THE GLOBAL STUDY

Assuming a 12-month site ramp-up period and a total of 200 sites, the global study is expected to be fully enrolled with approximately 600 patients (480 patients with detectable *PIK3CA*-mutant tumors and 120 patients without detectable *PIK3CA*-mutant tumors) by 28 months from the first patient enrolled in the study (FPI).

One efficacy and futility interim analysis for investigator-assessed PFS will be conducted in patients with detectable *PIK3CA*-mutant tumors when approximately 172 investigator-assessed PFS events (approximately 60% of information) have occurred in patients with *PIK3CA*-mutant tumors, which is expected to be reached at approximately 21 months after FPI.

The primary efficacy analysis for PFS will be conducted when 287 PFS events are observed in patients with *PIK3CA*-mutant tumors. This is expected to be reached at approximately 29 months after FPI.

Three interim analyses (time driven) and one final analysis (event driven) for OS are planned in patients with *PIK3CA*-mutant tumors: 1) the first interim analysis will be conducted at the time when both investigator-assessed PFS and ORR have reached their respective significance levels, so it could occur at the time of the interim efficacy or the final efficacy analysis for investigator-assessed PFS (approximately 21 or 29 months after FPI, approximately 63 or 118 OS events or 19% or 36% of OS information will be observed, respectively); 2) the second interim analysis will be conducted approximately 10 months after the first interim analysis; 3) the third interim analysis will be conducted approximately 8 months after the second interim analysis. The final analysis will be conducted after approximately 330 deaths are observed (approximately 77 months after FPI). Details are described in Section [4.4.2.2](#).

The China extension cohort is for China registration purpose only and will be reported separately from the global study. The CSR for the global study will include only results from the patients enrolled in the global portion of the study.

2.5 ANALYSIS TIMING FOR THE CHINA SUBGROUP

The analysis of PFS among Chinese patients will be performed when approximately 56 PFS events have occurred among the 150 Chinese patients with detectable *PIK3CA*-mutant tumors. A total of 56 PFS events in the China subpopulation will provide approximate 85% probability of observing at least 50% of the risk reduction in the PFS that is expected to be observed in the global population.

3. STUDY CONDUCT

3.1 RANDOMIZATION ISSUES

Eligible and consented patients will be randomized to receive either taselisib + fulvestrant or placebo + fulvestrant based on a 2:1 randomization ratio. Patients with and without detectable *PIK3CA*-mutant tumors will be randomized separately using a permuted block randomization method.

Randomization will be stratified by the following criteria:

- Visceral versus non-visceral disease
 - Visceral disease: metastatic disease in the lung, liver, adrenal glands, brain, heart, pericardium, pleura, peritoneum, or other end organs of the chest, abdomen, and pelvis
 - Non-visceral disease: absence of metastatic disease in visceral organs. Pleural effusions and/or ascites, disease involving lymph nodes, and disease involving bone are not considered to be visceral disease.
- Sensitivity versus non-sensitivity to the most recently administered endocrine therapy
 - Sensitive to most recently administered endocrine therapy:
 - For patients with no endocrine treatment in the advanced or metastatic setting, at least 24 months of adjuvant endocrine therapy prior to disease recurrence
 - Documented clinical benefit (complete response [CR], partial response [PR], or stable disease for • 24 weeks) to most recent endocrine treatment in the advanced or metastatic treatment setting
 - Non-sensitive: not satisfying the criterion to be sensitive
- Geographical region with 3 levels
 - Western Europe, United States, Canada, and Australia
 - Asia
 - Rest of the World

3.2 DATA MONITORING

An independent Data Monitoring Committee (iDMC) will monitor accumulating patient safety data for the global portion of the study. The iDMC will convene to review

cumulative safety data approximately every 6 months. The data on serious adverse events, death, and adverse events of special interest will be monitored by iDMC approximately every 3 months.

In addition, one efficacy and futility analysis for investigator-assessed PFS will be conducted in patients with *PIK3CA*-mutant tumors. The iDMC will review the data and may recommend stopping the study for efficacy or futility (details described in Section 4.8).

4. STATISTICAL METHODS

This section applies only to the global study. See Section 5 for the China subgroup analysis.

4.1 ANALYSIS POPULATIONS

4.1.1 Intent-to-Treat Population

The intent-to-treat (ITT) population includes all randomized patients regardless of whether they receive any amount of study treatment. Treatment assignment will be defined according to the treatment assigned at randomization by the interactive voice or Web response system (IxRS).

The ITT population will form the basis for efficacy analyses. The analyses for the primary and the secondary efficacy endpoints will be conducted in patients with *PIK3CA*-mutant tumors. These endpoints will also be evaluated in patients without detectable *PIK3CA*-mutant tumors as the exploratory analyses.

4.1.2 Safety Population

The safety population includes all randomized patients who receive at least one dose of taselisib or placebo or fulvestrant. Specifically, a patient will be included in the taselisib + fulvestrant arm in the safety analyses if the patient receives any amount of taselisib, regardless of the initial treatment assignment at randomization. The safety population will form the basis for safety analyses.

4.1.3 Pharmacokinetic Population

The pharmacokinetic population will include all patients who have received at least one dose of taselisib and provided valid (adequately documented dose time and pharmacokinetic sample time) pharmacokinetic assessments. The pharmacokinetic population at specific timepoints will vary, depending on the availability of results at confirmed dosing and pharmacokinetic assessment times.

4.2 ANALYSIS OF STUDY CONDUCT

Patient enrollment, duration of follow-up, and discontinuation from the study and discontinuation reasons will be summarized by treatment arm for all randomized patients. In addition, major protocol deviations, including violations of inclusion or exclusion

criteria, will be summarized by treatment arm. All the analyses will be performed separately for patients with and without detectable *PIK3CA*-mutant tumors.

4.3 ANALYSIS OF TREATMENT GROUP COMPARABILITY

The evaluation of treatment group comparability between the two treatment arms will include summaries of demographics, baseline disease characteristics (including *PIK3CA* mutation status), and patient treatment history.

Descriptive summaries of continuous data will present the group mean, SD, median, minimum, and maximum. Descriptive summaries of discrete data will present the category counts as frequencies and percentages.

All the analyses will be performed separately for patients with and without detectable *PIK3CA*-mutant tumors.

4.4 EFFICACY ANALYSIS

The stratification factors collected from the IxRS will be used in all the stratified analyses.

4.4.1 Primary Efficacy Endpoint

PFS is defined as the time from randomization to disease progression as determined by the investigator with the use of Response Evaluation Criteria in Solid Tumors Version 1.1 (RECIST v1.1) or death due to any cause, whichever occurs earlier. The primary PFS analysis will be conducted in all randomized patients with detectable *PIK3CA*-mutant tumors, with patients grouped according to the treatment arm assigned at randomization.

An interim efficacy analysis will be conducted for investigator-assessed PFS at the time of 172 investigator-assessed PFS events (expected 21 months after the first patient is enrolled), and the final efficacy analysis will be conducted at the time 287 investigator-assessed PFS events (expected 29 months after the first patient is enrolled) are observed in patients with *PIK3CA*-mutant tumors (see [Table 1](#)).

Table 1 Progression-Free Survival Analyses

	Estimated Timing (Clinical Data Cutoff)	PFS Events	Two-Sided p-Value Boundary	Rejection HR Boundary ^a	Percentage Information
PFS IA	~21 months after FPI	~172	$1.7 \cdot 10^{-5}$	0.5	60%
PFS FA	~29 months after FPI	~287	0.01	0.72	100%

FA=final analysis; FPI=first patient in; HR=hazard ratio; IA=interim analysis;
PFS=progression-free survival.

^a Assuming exponential distributions for the PFS event time of the two treatment arms.

The α -spending function is specified as Gamma ($\alpha = 16$), which allocates two-sided $\alpha = 1.7 \times 10^{-5}$ at the interim efficacy analysis of investigator-assessed PFS, when 172 PFS events have occurred, and preserves the two-sided 1% α -level at the final PFS analysis. The exact boundary will be calculated on the basis of the exact number of PFS events observed at the interim analysis. The associated minimal detectable difference for the investigator-assessed PFS HR at the interim efficacy analysis is 0.5 (i.e., 100% improvement in median investigator-assessed PFS from 4.5 months in the control arm to 9 months in the treatment arm).

Data from patients who are lost to follow-up or without disease progression or death as of the clinical data cutoff date will be censored at the time of the last tumor assessment when the patient is known to be progression-free (i.e., an overall response other than “progressive disease” or “not evaluable”) or at the time of randomization if there is no post-baseline tumor assessment or all post-baseline tumor assessments have overall responses of “not evaluable.”

For the US Food and Drug Administration (FDA), the primary efficacy analysis for investigator-assessed PFS will be censored additionally for patients experiencing a progression event preceded by two or more missing tumor assessments before the disease progression (i.e., the duration between the date of first documented progressive disease [PD] deemed by investigator per RECIST v1.1 and the date of the last tumor assessment when the patient is known to be progression-free > 122 days, i.e., $2 \times 8 \times 7 + 10$, given that the protocol allows tumor assessments to be conducted every 8 weeks \pm 5 days). These patients will be censored at the last tumor assessment prior to the missed visit that is known to be progression-free (i.e., an overall response other than “progressive disease” or “not evaluable”) or at randomization if there is no post-baseline tumor assessment or all post-baseline tumor assessments have overall responses of “not evaluable” in between the randomization and the first documented PD per RECIST v 1.1.

The two-sided log-rank test stratified by the three stratification factors will be used as the primary analysis to compare investigator-assessed PFS between the two treatment arms. The three stratification factors are: 1) visceral versus non-visceral, 2) sensitivity versus non-sensitivity to their most recently administered endocrine therapy, and 3) geographical region. The Kaplan-Meier method will be used to estimate median investigator-assessed PFS for each treatment arm. Cox proportional hazards models stratified by the three stratification factors will be used to estimate the HR and its 95% CI. The results from the unstratified log-rank test will also be provided.

4.4.2 Secondary Efficacy Endpoints

Assuming that the primary endpoint PFS is statistically significant, the first two secondary endpoints are planned to be tested in the following order:

- Overall ORR
- OS

4.4.2.1 Overall Objective Response Rate

Overall ORR is defined as a CR or PR as determined by investigator assessment using RECIST v1.1.

The analysis of ORR will only include patients with detectable *PIK3CA*-mutant tumors who have measurable disease per RECIST v1.1 at baseline as a secondary endpoint of the study and will be tested on the basis of a hierarchical testing procedure to preserve the type I error. That is, the ORR analysis will be conducted at the significance level of two-sided 5% at the time that a statistically significant benefit is observed for the investigator-assessed PFS at either the interim efficacy or final PFS analysis.

An estimate of the response rate and its 95% CI will be calculated using the Blyth-Still-Casella method for each treatment arm. Response rates in the treatment arms will be compared using the stratified Mantel-Haenszel test. The CI for the difference in ORRs between the two treatment arms will be determined using the normal approximation to the binomial distribution. To be conservative, patients with no post-baseline tumor assessments or with post-baseline tumor assessments that have overall responses of “not evaluable” will be considered to be non-responders.

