4.4.2.2 Overall Survival

OS is defined as the time from randomization to death from any cause. The analysis for OS will be conducted only in all randomized patients with detectable *PIK3CA*-mutant tumors as a secondary endpoint of the study and will be tested based on a hierarchical testing procedure to preserve type I error. That is, the OS will be tested only if both investigator-assessed PFS and ORR have reached their respective significance levels. The overall type I error for OS is preserved at two-sided 5%.

OS will be analyzed with patients grouped according to the treatment arm assigned at randomization. Data from patients who are alive at the time of the analysis data cutoff will be censored at the last date they are known to be alive. Data from patients without post-baseline information will be censored at the date of randomization.

The analyses will be conducted using the stratified two-sided log-rank test, and the results from the unstratified log-rank test will also be provided. The OS curve for each treatment arm will be estimated by the Kaplan-Meier method, and the HR and its 95% CI will be estimated by Cox proportional hazards models.

Three interim analyses (time driven) and one final analysis (event driven) for OS are planned in patients with detectable *PIK3CA*-mutant tumors (see [Table 2](#) and [Table 3](#)):

- The first interim OS analysis will be conducted at the time when both investigator-assessed PFS and ORR have reached their respective significance levels, so it could occur at the time of the interim efficacy or the final efficacy analysis for investigator-assessed PFS.
- The second interim analysis will be conducted approximately 10 months after the first interim analysis.
- The third interim analysis will be conducted approximately 8 months after the second interim analysis.
- The final analysis will be conducted after approximately 330 deaths are observed (approximately 77 months after FPI).

Table 2 Interim Analyses for Overall Survival if the First Interim Overall Survival Analysis Occurs at the Time of the Interim Efficacy Analysis of Investigator-Assessed Progression-Free Survival

	Estimated Timing (Clinical Data Cutoff)	OS Events	Two-Sided p-Value Boundary	Rejection HR Boundary ^a	Percentage Information
First OS IA	~21 months after FPI	~63	0.001	0.44	19%
Second OS IA	~10 months after first OS IA	~134	0.010	0.65	41%
Third OS IA	~8 months after second OS IA	~188	0.045	0.75	57%

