4.4.2.3 Clinical Benefit Rate

Clinical benefit is defined as overall objective response (CR or PR) or no disease progression for \geq 24 weeks after randomization as determined by investigator tumor assessments using RECIST v1.1. The analysis of CBR will be performed for patients with detectable *PIK3CA*-mutant tumors with measurable disease per RECIST v1.1 at baseline and will be repeated for the group of patients with detectable *PIK3CA*-mutant tumors regardless of measurable disease at baseline. To be conservative, patients with no post-baseline tumor assessment or with post-baseline tumor assessments that have overall responses of “not evaluable” will be considered to not experience clinical benefit.

An estimate of CBR and its 95% CI will be calculated using the Blyth-Still-Casella method for each treatment arm. The CBRs in the treatment arms will be compared using the stratified Mantel-Haenszel test. The CI for the difference in CBRs between the two treatment arms will be determined using the normal approximation to the binomial distribution.

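### ORR and CBR are compared with a stratified test, but the interval for the difference ignores the strata and is modestly too wide if they are prognostic; the OS Cox model should be labelled as stratified.

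*Combined protocol and SAP*

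**What the plan says.** For ORR, SAP 4.4.2.1 specifies the test: "Response rates in the treatment arms will be compared using the stratified Mantel-Haenszel test". For the size of the effect it says: "The CI for the difference in ORRs between the two treatment arms will be determined using the normal approximation to the binomial distribution". It mentions no strata or weights for that interval and gives no confidence level.

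For CBR, SAP 4.4.2.3 follows the same pattern: "The CBRs in the treatment arms will be compared using the stratified Mantel-Haenszel test", and then "The CI for the difference in CBRs between the two treatment arms will be determined using the normal approximation to the binomial distribution".

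For OS, SAP 4.4.2.2 says "The analyses will be conducted using the stratified two-sided log-rank test", adds that the unstratified test will also be reported, and then says "the HR and its 95% CI will be estimated by Cox proportional hazards models". Whether that model is stratified is not stated. For PFS, by contrast, SAP 4.4.1 writes: "Cox proportional hazards models stratified by the three stratification factors will be used to estimate the HR and its 95% CI".

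Protocol 6.4.2.1 to 6.4.2.3 are worded in the same way as the SAP on these points, and SAP section 1 gives the SAP precedence over the protocol's statistics section.

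**The concern.** The trial randomises 2:1 within strata defined by three factors and carries those factors into its tests. If the factors predict response, stratified randomisation removes most of the chance imbalance between arms in those factors. A plain two-sample interval still counts the variation between strata as noise, so it overstates the uncertainty of the difference. It also puts the reported difference on another basis from the test printed beside it.

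What is at stake is the precision and clarity of two reported secondary estimates. For OS it is which hazard ratio is meant, given that both a stratified and an unstratified log-rank result are to be reported and only one Cox result is described.

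**Working it through.** **Step 1. Test and estimate side by side.** The plan states no figure that depends on this choice, so there is none to reproduce; the first check is of the text.

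| Endpoint (SAP section) | Test | Effect estimate |
|---|---|---|
| PFS (4.4.1) | stratified log-rank | Cox, stratified by the three factors |
| ORR (4.4.2.1) | stratified Mantel-Haenszel | difference, normal approximation, no strata named |
| OS (4.4.2.2) | stratified log-rank | Cox, strata not mentioned |
| CBR (4.4.2.3) | stratified Mantel-Haenszel | difference, normal approximation, no strata named |
| BICR-assessed PFS (4.4.2.5) | as for PFS | Cox, stratified by the three factors |
| Time to deterioration (4.4.2.6) | none given | Cox, stratified by the three factors |
| China subgroup PFS (5) | unstratified log-rank, descriptive | Cox, written as unstratified |

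The opening sentence of SAP 4.4 says where the factors come from (IxRS) for analyses that are stratified. It does not say which analyses are, so it does not make the ORR and CBR intervals stratified.

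**Step 2. Why the plain interval is too wide.** With stratum response rates p_k and overall rate p, the binomial variance splits as

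p(1 − p) = mean of p_k(1 − p_k) + variance of p_k between strata.

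When randomisation balances the strata, the second term no longer contributes to the variance of the difference, but the plain formula still includes it.

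Hand example. All inputs are assumed; the documents give neither the number of patients with measurable disease nor stratum response rates. Take 360 measurable patients split 240:120, two equal strata with control response 5% and 25%, and a 12-point difference in each (17% and 37% on taselisib).

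- Control: overall 0.15 × 0.85 = 0.1275; within strata (0.0475 + 0.1875)/2 = 0.1175.
- Taselisib: overall 0.27 × 0.73 = 0.1971; within strata (0.1411 + 0.2331)/2 = 0.1871.
- Unstratified SE = √(0.1971/240 + 0.1275/120) = √0.001884 = 0.0434.
- Stratified SE = √(0.1871/240 + 0.1175/120) = √0.001759 = 0.0419.
- Ratio = √(0.001884/0.001759) = 1.035, so about 3.5% too wide. A nominal 95% interval then covers about 2Φ(1.96 × 1.035) − 1 = 95.7%.

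A simulation with four strata, control response 5-25% and the same 12-point difference gave 0.0421 against 0.0409, a ratio of 1.029.

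**Step 3. The design's own strata.** SAP 3.1 gives 2 × 2 × 3 = 12 cells. Simulation with 12 cells, 2:1 allocation and assumed rates, with the strength of the strata expressed as the SD of stratum log-odds:

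- SD 0.8 (strongly prognostic): unstratified SE about 3-6% larger.
- SD 0.5: about 1.5-3% larger.
- Coverage of the unstratified interval mostly 95-96%, against about 95% for the stratified one.

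**Step 4. Does stratifying the interval make it agree with the test?** Share of simulated trials in which the stratified test and the 95% CI disagree at two-sided 5%, with stratum SD 0.8 unless stated:

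| Assumed rates | Unstratified CI | Mantel-Haenszel-weighted CI |
|---|---|---|
| 10% vs 20%, 360 patients | 3.0% | 4.4% |
| 15% vs 27%, 360 patients | 2.4% | 3.7% |
| 10% vs 20%, 300 patients | 3.6% | 5.6% |
| 10% vs 20%, 360 patients, SD 0 | 4.9% | 5.0% |
| 40% vs 52% (clinical-benefit range) | 3.4% | 1.0% |

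At response rates in an ORR range, agreement does not improve. At CBR-type rates it does. Disagreement remains at SD 0, where strata are irrelevant, so much of it must come from elsewhere: the test uses a variance under the null and the interval does not.

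**Step 5. OS.** With assumed stratum log-hazard SD from 0 to 0.7, true HR 0.70, and 188 or 330 deaths, the mean HR was 0.69-0.70 from a stratified Cox model and 0.69-0.73 from an unstratified one. At two-sided 5%, the stratified log-rank test disagreed with the unstratified Cox CI in about 2-11% of trials, and with the stratified Cox CI in at most 0.2%.

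**The case against.** The strongest objection is that the tests, not the intervals, carry the inference. ORR opens the way to OS through its significance level, so type I error, power and gatekeeping are untouched. This stands in full. CBR is not in the hierarchy at all: SAP 4.4.2 lists only ORR and OS.

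A reader might infer that the plain interval will contradict the test and that stratifying it would cure this. Step 4 does not support that for ORR, where the weighted interval disagreed slightly more often. Nor does too wide mean that the interval will mainly miss effects that the test finds. In simulations where the arms differed, the commoner disagreement was usually an interval excluding zero beside a non-significant test.

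A reader might also infer that the OS hazard ratio is planned as unstratified. SAP 4.4.2.2 does not say so; it is silent, and a stratified model is compatible with its wording. Nor would stratifying make the 95% CI the counterpart of the formal OS test. The OS boundaries in SAP Tables 2 and 3 are 0.001, 0.010, 0.045 and 0.007 or 0.013, and Protocol Tables 12 and 13 keep only 0.001 and 0.010. None is 5%, so the 2-11% in step 5 is not an error rate at any planned look.

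Finally, the unstratified difference is a valid, mildly conservative estimate, and every size given here rests on assumed rates. That stands, and it is why the point is minor.

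**Conclusion.** The point holds as a matter of precision and consistency. For ORR and CBR the plan tests within strata but describes the difference without them. The resulting interval is modestly too wide when the strata predict outcome: about 3-6% in standard error if they are strongly prognostic, about 1.5-3% if moderately so, and not at all if they are unrelated to response. These figures assume 12 strata, 2:1 allocation, about 300-400 measurable patients and response rates that the documents do not give.

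For OS the finding is only that the model is unlabelled where the other Cox models are labelled. It is a clarification, not evidence of an unstratified analysis. The documents do not support reading any of this as a threat to the formal tests. Severity is low.

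**What to change.** In SAP 4.4.2.1 and 4.4.2.3, make the main estimate the risk difference weighted over the IxRS strata with Mantel-Haenszel weights, w_k = n_1k n_0k/(n_1k + n_0k), where n_1k and n_0k are the arm sizes in stratum k. Give a 95% CI, state that level, and name a variance estimator suited to sparse cells, such as Sato's, because some of the 12 cells may be small. Keep the unstratified interval as supportive and label it so. Do not promise that interval and test will always agree.

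In SAP 4.4.2.2, add that the OS Cox model is stratified by the three IxRS factors; an unstratified HR can accompany the unstratified log-rank result. Make the same changes in Protocol 6.4.2.1 to 6.4.2.3.

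The cost is a few sentences and about one line of code per endpoint, with no new data. The protocol amendment reports that the primary PFS analysis took place in January 2018. If ORR and CBR were analysed then, add the stratified difference, mark it as added afterwards, and label the existing interval as unstratified. The OS wording can still be settled before the one further OS analysis described in Protocol 6.4.2.2, if that has not yet been run.
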